OBSERVATIONAL PLAN OF THE NON-INTERVENTIONAL STUDY (NIS) ESCALATE-RA

Study information

Title	ESCALATE-RA A NON-INTERVENTIONAL STUDY OF CRITICAL FACTORS FOR ESCALATING DRUG TREATMENT IN PATIENTS TREATED WITH TOFACITINIB FOR MODERATE TO SEVERE ACTIVE RHEUMATOID ARTHRITIS
Protocol number	A3921302
Protocol version identifier	Final 1.1
Date of last version of protocol	23-Aug-2017
Active substance	L04AA29 Tofacitinib
Medicinal product	Xeljanz®
Research question and objectives	The objective of this non-interventional study is to identify key factors that are driving treatment decisions by rheumatologists in the treatment of rheumatoid arthritis (RA) patients starting treatment with Tofacitinib in a real world setting. In addition to disease activity score (DAS) 28, the following factors may play an important role: difference between DAS28 at start of therapy and after 3-6 months, physician's global assessment of disease activity, patients' global assessment of disease activity, arthritis pain and patient

	satisfaction with drug treatment.
Author	PPD

Table 1 Study information

This document contains confidential information belonging to Pfizer. Except as otherwise agreed to in writing, by accepting or reviewing this document, you agree to hold this information in confidence and not copy or disclose it to others (except where required by applicable law) or use it for unauthorized purposes. In the event of any actual or suspected breach of this obligation, Pfizer must be promptly notified.

TABLE OF CONTENTS

TABLE OF CONTENTS.....	3
1. LIST OF ABBREVIATIONS.....	6
2. RESPONSIBLE PARTIES	9
3. AMENDMENTS AND UPDATES.....	10
4. MILESTONES.....	11
5. RATIONALE AND BACKGROUND.....	11
6. RESEARCH QUESTION AND OBJECTIVES	12
6.1. Endpoints.....	13
6.1.1. Primary Endpoint:.....	13
6.1.2. Secondary Endpoints:	13
7. RESEARCH METHODS	14
7.1. Study design	14
7.2. Setting.....	14
7.2.1. Inclusion criteria	15
7.2.2. Exclusion criteria	15
7.3. Variables.....	16
7.4. Data sources	18
7.5. Study procedure.....	18
7.5.1. Study Period.....	19
7.5.2. Schedule of Activities.....	23
7.6. Assessments	25
7.6.1. Physical Examination	25
7.6.2. Prognostic Factors	25
7.6.3. Insurance Type.....	25
7.6.4. Varicella vaccination status	25
7.6.5. Treatment of Rheumatoid Arthritis (RA-Treatment) with Tofacitinib and/or other DMARDs.....	25
7.6.6. Concomitant treatment for rheumatoid arthritis with glucocorticoids	25
7.6.7. Effectiveness criteria	26
7.6.8. Joint Counts	26

1. LIST OF ABBREVIATIONS

Abbreviation	Definition
ACPA	Anti-citrullinated protein antibodies
ACR	American Colleague of Rheumatology
AE	Adverse Event
AEM	Adverse event monitoring
AMS	Advanced Medical Services GmbH
BfArM	Bundestinstitut für Arzneimittel und Medizinprodukte (German Federal Institute for Drugs and Medical Devices)
CAPEA	Course and Prognosis of Early Arthritis
CDAI	Clinical Disease Activity Index
CFR	Code of Federal Regulations
CIOMS	Council for International Organizations of Medical Sciences
CRA	Clinical Research Associate
csDMARD	Conventional Synthetic Disease Modifying Antirheumatic Drug
eCRF	Electronic Case Report Form
CRP	C-reactive Protein
DAS	Disease Activity Score
DMARD	Disease Modifying Antirheumatic Drug
EDC	Electronic Data Capture
EDP	Exposure during pregnancy

EMA	European Medicines Agency
ENCePP	European Network of Centres for Pharmacoepidemiology and Pharmacovigilance
EQ-5D	a self-report questionnaire (a quality of life instrument) developed by the European Quality of Life (EuroQoL) Group
ESR	Erythrocyte sedimentation rate
EULAR	European League Against Rheumatism
EuroQoL	European Quality of Life [Group]
FACIT	Functional Assessment of Chronic Illness Therapy
FFbH	Functional Ability Questionnaire Hannover
GEP	Good Epidemiological Practice
GPP	Good Pharmacoepidemiology Practices
HCP	Healthcare Professional
IEA	International Epidemiological Association
IEC	Independent Ethics Committee
IR	Incidence Rate
ISPE	International Society for Pharmacoepidemiology
ISPOR	International Society for Pharmacoeconomics and Outcomes Research
JAK	Janus-kinase
LDA	Low disease activity
MCP	Metacarpophalangeal joint
MTX	Methotrexate
NIS	Non-Interventional Study

PEI	Paul-Ehrlich Institut
PhyGA	Physician Global Assessment of Arthritis
PIP	Proximal interphalangeal joints
PtGA	Patient Global Assessment of Arthritis
PY	Patient years
RA	Rheumatoid arthritis
RF	Rheumatoid factor
SAE	Serious Adverse Events
SAP	Statistical Analysis Plan
SDAI	Simplified Disease Activity Index
SJC	Swollen Joint Count
SmPC	Summary of Product Characteristics
SSL	Secure Sockets Layer
TJC	Tender Joint Count
TNF	Tumor necrosis factor
VAS	Visual Analogue Scale
Vfa	Verband der forschenden Pharma-Unternehmen [German Association of Research-Based Pharmaceutical Companies]

Table 2 List of Abbreviations

3. AMENDMENTS AND UPDATES

Amendment number	Date	Substantial or administrative amendment	Protocol section(s) changed	Summary of amendment(s)	Reason
1	23 – Aug-2017	Substantial	4, 7, 9	
Start of data collection in OctoberAdd Insurance Type as confounderSpecify patient's satisfaction with drug treatmentCorrect number of monitoring visitsCorrect safety reporting to CRO AMS instead of PfizerClarify that all events (both with Xeljanz® and DMARDs of other manufacturers) have to be reported	Update of timelines, change of confounders and correction/specification of safety reporting process

Table 4 Amendments and Updates

4. MILESTONES

Milestone	Planned date
Completion of feasibility assessment	28-July-2017
Start of data collection	23-October-2017
End of data collection	23-October-2022
Final study report	23-October-2023

Table 5 Milestones

5. RATIONALE AND BACKGROUND

Rheumatoid arthritis (RA) is a chronic autoimmune disease characterized by joint inflammation and destruction, progressive disability and adverse psychological effects.[1] Apart from musculoskeletal complications, RA patients suffer from increased frequencies and impacts of comorbidities such as cardiovascular and infectious diseases, osteoporosis or cancer, leading to higher mortality rates.[2,3,4] In addition, RA represents significant health and socioeconomic burdens for the individual patient and society, especially with regard to work disability and work productivity loss.[5,6]

With currently no curative therapy available, treatment strategies aim at controlling disease activity, alleviating signs and symptoms, maintaining physical function, improving quality of life, reducing the rate of joint damage, and, if possible, inducing complete remission.

Best treatment outcomes are achieved if RA is treated with disease modifying antirheumatic drugs (DMARDs) right from the beginning ('hit hard and early', 'window of opportunity').[7,8,9,10] Furthermore, treatment strategies that aim at a predefined target ('treat-to-target' concept) have been shown to be superior to former, traditional approaches ('wait and see').[11] Therefore, current European League Against Rheumatism (EULAR)-recommendations and the German S1 guideline derived from the EULAR-recommendations define treat-to-target as the basic therapeutic principle. The target to aim for is remission, especially in DMARD-naïve patients, or low disease activity, primarily in patients who failed previous therapies.[12] Although criteria for RA remission vary substantially in studies and clinical practice, the 28-joint Disease Activity Score (DAS28) is traditionally being widely

used where $DAS28 < 2,6$ defines remission and $DAS28 \leq 3,2$ low disease activity.[13] According to EULAR recommendations, therapy has to be adjusted until the treatment target has been reached.

How is the treat to target approach applied in everyday care?

Despite insufficient response after 3 to 6 months therapy, treat-to-target recommendations of EULAR were only applied in 50% of the German course and prognosis of early arthritis cohort (CAPEA).[14] In an analysis of a cohort from the “Kerndokumentation”, a national database of the German Collaborative Arthritis Centres, 45% of patients were not within DAS28 low disease activity range and therefore would have needed adaption of therapy according to current treatment guidelines. In contrast, rheumatologists’ global assessment of disease activity differed, 80% perceived their patients to be in the low disease activity range and, hence, as being adequately treated.[15]

These observations suggest that in a real-world setting, criteria other than calculated DAS28 remission or low disease activity alone may guide treatment decisions. Among such criteria, satisfaction with drug treatment is of particular interest. On the one hand, a patient who is content with his current therapy is less likely to be willing to change a therapy solely to achieve a better DAS28 score. On the other hand, patient preference and satisfaction of a therapy strongly affects adherence to a prescribed medication, ultimately affecting treatment outcome and efficacy. A factor known to impact on patient satisfaction with a prescribed treatment is the route of administration. Here, several studies point to a preference for oral therapies, also among second-line DMARDs.[16,17]

Recently, Tofacitinib, an orally applied DMARD of the new class called Janus-Kinase-Inhibitors (JAK-Inhibitors) has been brought into the market in the European Union. Tofacitinib is indicated in combination with methotrexate (MTX) for the treatment of moderate to severe active rheumatoid arthritis (RA) in adult patients who have responded inadequately to, or who are intolerant to one or more DMARD. Due to oral administration of Tofacitinib, the impact of patient’s satisfaction with drug treatment on therapy decisions by rheumatologists may be especially pronounced.

EULAR recommendations have now endorsed individual patient related factors such as patient preferences and comorbidities as an overarching principle in the management of RA.

6. RESEARCH QUESTION AND OBJECTIVES

The objective of this non-interventional study is to identify key factors that are driving treatment decisions by rheumatologists in the treatment of RA patients starting treatment with Tofacitinib in a real world setting. In addition to DAS28 score, the following factors may play an important role: difference between DAS28 at start of therapy and after 3-6 months, physician’s global assessment of disease activity, patient’s global assessment of disease activity, arthritis pain and patient’s satisfaction with drug treatment.

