7.7. Study size

The analysis of the primary endpoint is a time to event analysis, where the event is treatment escalation. It is possible for multiple events to occur for each patient within the follow-up period. The primary analysis aims to investigate which of the factors listed actually affect the rate at which a patient's treatment is changed. In order to determine an appropriate sample size for this study recurrent event data was simulated, using the methods described by Jahn-Eimermacher *et al.* (2015), and analysed using cox proportional-hazards models.[21]

The distribution of each of the factors was obtained from the ORAL STANDARD study:

Achieve DAS28 < 3.2	-	Binomial(n, 0.2)
Achieve Δ DAS28 > 1.8	-	Binomial(n, 0.6)
Δ Patient Global Assessment	-	Normal(-29.31, 38.579 ²)
Δ Physician Global Assessment	-	Normal(-27.01, 30.966 ²)
Δ Pain score	-	Normal(-34.99, 24.672 ²)

The baseline hazard rate was assumed to be 3.16 events per patient over the follow-up period.

The impact of each the factors on the hazard rate, (entered as the regression coefficient), is used to simulate the event times for each patient given their values for the simulated factors. The regression coefficients were assumed to be (-0.288, -2.303, -0.01, -0.01, -0.01). Simulations were carried out for sample sizes ranging from 100 to 4,500.

Figure 2 shows the power to detect an effect of each factor against sample size for the 5 different factors.

[figure not shown]

Figure 2: Plot of Power against Sample Size for simulations of recurrent event data analysed using cox-proportional hazards model including all 5 factors of interest.

Given the initial assumptions the power to detect an impact of 4 of the 5 factors, within the full cox proportional hazards model was greater than 80% with a sample size of 1000 patients. The power to detect an effect of the remaining factor, achieving $DAS28 \leq 3.2$, was around 50% for 1500 patients and 60% for 2000 patients. The power is very high for $\Delta DAS28 > 1.8$, mainly due to the high proportion of patients assumed to achieve the criteria and the high impact achieving the criteria is assumed to have on the rate of treatment escalation (significantly reducing it).

Sensitivity analyses were carried out around the assumptions made for the simulations. Full details of the sensitivity analyses will be included in the SAP.

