7.12. Limitations of the research methods

Randomised controlled trials are important and powerful tools in assessing efficacy and safety but have their limitations in terms of generalisability. In order to assess health economics, clinical effectiveness and safety of Tofacitinib in a usual care setting, parameters need to be determined by performing observational studies.

Inherent limitations of non-interventional, observational, non-controlled, non-randomised studies in general are the risk of selection/ascertainment bias and some lack of a parallel control group, which complicate the interpretation of the causality between treatment and outcomes. Furthermore, as with any "as observed" analysis, there is a potential risk of bias due to missing outcome data; the risk increases with increasing number of missing outcome data.

As data captured will be limited to information available from the physician participating in the study under a usual care setting, there is a greater possibility that there will be individual items of missing data (e.g. CRP not measured or FFbH questionnaire not completed). Following up patients after treatment escalation, rather than discontinuing patients from the study when they switch from Tofacitinib, should result in a higher proportion of the patients remaining in the study until the planned completion date. Where data are missing, information from the patient at other visits may be used in the primary analysis model to assess predictors of treatment decisions. If the different factors being considered in the primary statistical model to look at impact of treatment change are highly correlated it may not be clear which of the factors is in fact driving the rate of treatment escalation. Other sensitivity analyses may be explored to assess the impact of any confounding. Further details will be included in the SAP.

Patients selected for study inclusion represent a population who are initiated on Tofacitinib as part of a usual care setting. The sample of patients will be obtained from physicians who are willing to participate in the study and there is a possibility that certain types of patients will be selected to be prescribed Tofacitinib (selection bias) and join the study and this could potentially have an impact on findings of the primary analysis (if the 'type' is expected to impact the rate of treatment escalation). Therefore, study findings may not be generalizable to all RA patients.

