7.3 COVARIATES, FACTORS AND POTENTIAL CONFOUNDERS

7.3.1 FACTORS OF INTEREST FOR PRIMARY ANALYSIS

The following covariates will be included in the primary analysis:

- a. DAS 28-4 (ESR) LDA (see sections 6.1.2.4.1 and 6.1.2.2.3 for derivations) [Note: this is a binary endpoint].
- b. Indicator variable for whether patient has achieved change from baseline of DAS28-4 (ESR) > 1.8 (see section 6.1.2.4.1 for derivations of DAS28-4 (ESR)) [Note: this is a binary endpoint].

Change from baseline will be calculated as:

$\Delta\text{DAS28-4 (ESR)} = \text{DAS28-4 (ESR) at time point} - \text{DAS28-4 (ESR) at baseline}$

If a patient has achieved $\Delta\text{DAS28-4 (ESR)} > 1.8$ the indicator will be 1,

If $\Delta\text{DAS28-4 (ESR)} > 1.8$ is not achieved, the indicator will be 0.

- c. Physician Global Assessment of Arthritis – measured on a visual analogue scale (0-100mm).
- d. Patient's Global Assessment of Arthritis – measured on a visual analogue scale (0-100mm).
- e. Patient's Assessment of Arthritis Pain – measured on a visual analogue scale (0-100mm).
- f. Patient's overall satisfaction with treatment:

For each patient the response to the question ‘How satisfied are you with the drugs that you have received for your arthritis since your last visit?’ will be assigned as below:

0 = extremely dissatisfied,

1 = dissatisfied,

2 = neither satisfied nor dissatisfied,

3 = satisfied

4 = extremely satisfied

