9.1.1 ANALYSIS FOR RECURRENT EVENT DATA

In order to account for the possibility that there are multiple events occurring for each patient cox-proportional hazards modeling will be used with adjustment for recurrent events. This involves fitting either the Andersen and Gill or Prentice, Williams and Peterson gap-time models to the data.

For each patient, the data will be split into time periods, then data for each time window should include the patient's status, the time of event (if the event occurred) and the value of each of the factors of interest:

So, for patient A, who had events at M6 and M18, their data could look like this:

Patient	Start	Stop	Treatment Escalation Status	Factor A	Factor B	Factor C
A	0	M6	1	3.9	0.6	-10
A	M6	M12	0	3.0	1.5	-20
A	M12	M8	1	2.8	1.7	-10
A	M18	M24	0	2.2	2.3	-10

The cox proportional hazards model (using PROC PHREG) is then used, including the factors of interest (Section 7.3.1) to determine which, if any of them, have an impact on the rate at which treatment changes occur.

Any potential confounders should be included in the model also (Section 7.3.3).

The estimated event rate will be presented, along with 95% confidence interval and p-value, for each of the covariates of interest. Note: These will not be presented for the variables considered to be confounders.

The number and proportion of people experiencing an event at each time point will be presented.

Supportive tables will also be presented which summarises each of the covariates in the model at each visit.

The analysis will be performed for each type of escalation as defined in section 7.1.1 and overall.

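### The study asks whether criteria beyond DAS28 guide escalation, but the SAP plans no joint test of what physician global, patient global, pain and satisfaction add together, and sets no reporting increment for them

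*Protocol*

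**What the plan says.** Protocol section 5 argues that rheumatologists may be guided by criteria other than the calculated DAS28. Section 6 turns this into the objective: "The objective of this non-interventional study is to identify key factors that are driving treatment decisions by rheumatologists". It continues: "In addition to DAS28 score, the following factors may play an important role".

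SAP 7.3.1 enters six factors on three scales: two 0/1 indicators derived from DAS28-4 (ESR), three visual analogue scales and one 0-4 satisfaction score. A typical entry is "Physician Global Assessment of Arthritis – measured on a visual analogue scale (0-100mm"). All six go into one recurrent-event Cox model with the confounders of SAP 7.3.3. The model is used "to determine which, if any of them, have an impact on the rate at which treatment changes occur", and the output is fixed in SAP 9.1.1: "The estimated event rate will be presented, along with 95% confidence interval and p-value, for each of the covariates of interest".

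Protocol 7.12 warns that if the factors are highly correlated, "it may not be clear which of the factors is in fact driving the rate of treatment escalation". In response, SAP 9.2.2 offers an exploration of collinearity without a stated method, and SAP 7.3.2 a sensitivity model with DAS28 and its change as continuous terms. Neither document states a joint or nested test, a reporting increment, or a criterion for calling a factor key.

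**The concern.** Protocol section 5 poses a question about a group: do criteria other than DAS28 guide decisions? The planned output consists of six separate tests. When several factors share information, each one's adjusted estimate is imprecise, and separate tests can all miss an effect that the group clearly carries. Overlap is partly built in: patient global is a component of DAS28 (SAP 7.1.2.4.1) as well as a covariate of its own.

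The opposite error is also possible. If one significant result among the four non-DAS28 factors were taken as a yes, the false-positive rate with independent tests at 0.05 would be 1 − 0.95⁴ = 18.5%.

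A smaller matter is presentation. Without a stated increment, a hazard ratio per millimetre stands beside a 0-to-1 contrast, and a reader may take the size of the number as a measure of importance.

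**Working it through.** **1. The plan's own figures.** The plan gives no figure for a joint test. Its only power figures are per factor (Protocol 7.7), including around 50% at 1500 patients for DAS28 ≤ 3.2. Simulating the stated inputs (3.16 events per patient, independent factors, two-sided 0.05 assumed) gave about 100%, so the figure was not reproduced. In the Schoenfeld formula, 50% power for that factor corresponds to 1.96² / (0.2 × 0.8 × 0.288²) = 3.84 / 0.01327 ≈ 290 events. In the simulations the stated pattern returned only at about 0.23 events per patient (0.23 × 1500 = 345 events) or with strong between-patient heterogeneity. This is a separate matter and does not decide the point, but it makes 300 events a reasonable low scenario against 3.16 × 1500 = 4,740.

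**2. Single tests against a joint test.** Assumptions, none of them in the documents:

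- Hazard ratio 1.10 per SD for each of the four factors, in the direction of worse state or lower satisfaction (log 0.0953).
- Correlation r among the three visual analogue scales 0.60 or 0.75, and 0.45 between each of them and satisfaction.
- Correlation 0.5 between the scales and each DAS28 term, 0.3 between satisfaction and each DAS28 term, and 0.5 between the two DAS28 terms.
- Information = events × correlation matrix; two-sided 0.05.

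Single factor: z = 0.0953 × √(events × (1 − R²)), where R² comes from regressing that factor on the other five.

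- r = 0.60, each scale: 1 − R² = 0.499; z = 0.0953 × √149.7 = 1.17; power 21%.
- r = 0.75, each scale: 1 − R² = 0.342; z = 0.0953 × √102.5 = 0.96; power 16%.
- Satisfaction: 1 − R² = 0.724 or 0.755; power 29% or 30%.

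Joint test: noncentrality = events × b′Sb, where S is the correlation matrix of the four factors given both DAS28 terms. At 300 events this is 16.3 (r = 0.60) or 18.7 (r = 0.75), against a 4-df critical value of 9.49. The chance that no factor is significant comes from 200,000 multivariate normal draws.

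| Events | r | No single factor significant | 4-df power |
|---|---|---|---|
| 300 | 0.60 | 27% | 92% |
| 300 | 0.75 | 36% | 95% |
| 600 | 0.60 | 5% | >99% |
| 600 | 0.75 | 11% | >99% |
| 1000 | 0.60 | 0.2% | >99% |
| 1000 | 0.75 | 1% | >99% |

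**3. Where the gain disappears.**

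- Protocol planning effects (0.01 per mm × planning SD: 0.386, 0.310, 0.247) with 300 events: single-scale power is about 70% to above 99%, and the chance of no significant factor is about 0.
- Planning effects and planned event rate: every test has about 100% power.
- All correlations zero, 300 events, hazard ratio 1.10: the joint test has 76% power against 85% for at least one significant factor.

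A separate simulation of the three scales alone (1500 patients, rate 0.18, assumed −0.003 per mm) shows the same pattern. Joint power against at least one significant factor was 46% v 62% at r = 0, 80% v 40% at r = 0.7, and 85% v 20% at r = 0.9.

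**4. Increment.** Protocol 7.7 states: "The regression coefficients were assumed to be (-0.288, -2.303, -0.01, -0.01, -0.01"). On these values the low-disease-activity indicator has a 0-to-1 log effect of 0.288. Pain has 0.01 per mm, 0.01 × 24.672 = 0.247 per SD, and 0.01 × 1.349 × 24.672 = 0.333 per interquartile range (assuming normality). Pain therefore falls below or above the indicator depending on the increment chosen.

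**The case against.** **The separate tests already measure what each factor adds.** A reader might infer that the plan does not test anything beyond DAS28. The documents do not support that. Both DAS28 indicators are in the same model, so every other factor's p-value is conditional on them. In simulation, the per-factor Wald decision agreed with the 1-df likelihood-ratio test of adding that factor in 99.7-100% of tests. Only the joint test is absent.

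**No ranking is promised.** Protocol 6.1.1 speaks of impact, and SAP 9.1.1 asks which factors, if any, have one. A ranking is at most inferred from the word key, so its absence is not a defect.

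**A scale reversal is tempting but does not carry over.** A reader might infer that raw coefficients would make low disease activity look dominant and put the factors in the wrong order. The change-in-DAS28 indicator, at −2.303, is the largest planning effect both as it stands and per SD (2.303 × √(0.6 × 0.4) = 1.128). The planning SDs describe change scores, whereas SAP 7.3.1 enters absolute values. The SAP names no unit, and the table shells (SAP section 10) are a separate document not available here.

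**A joint test does not answer everything.** Protocol 5 singles out satisfaction, which needs its own estimate. Protocol 6 lists the DAS28 difference among the additional factors, while the joint test places it on the DAS28 side. Both are fair; they are reasons to keep the factor-wise estimates, not to omit the joint test.

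**The scenario is unfavourable by choice.** This stands, as step 3 of the working shows.

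**Conclusion.** The point holds as a low-cost improvement, not as an error in the planned model. The SAP has no joint test or measure of what the four non-DAS28 factors contribute together, although the rationale asks that question and the protocol foresees that correlated factors may be inseparable. No reporting increment is stated.

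The gain is conditional. It is large with few events, modest effects and correlated factors (27-36% of studies with no significant factor, against 92-95% joint power), small by 600 events (5-11%) and nil under the protocol's planning values. It reverses if the factors are uncorrelated. Correlations, effect sizes, event counts and alpha are assumptions, and the calculation ignores clustering of rows within patients, which would lower the effective number of events. The SAP also repeats the analysis by escalation type, where events will be fewer than overall.

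It should not be read as showing that the planned p-values ignore DAS28, or that the study is likely to order its factors wrongly.

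**What to change.** In SAP 9.1.1 and 9.2.2, before results are seen:

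1. Pre-specify one 4-df robust Wald test, clustered by patient, of physician global, patient global, pain and satisfaction, given the confounders and both DAS28 terms. Repeat it in the SAP 7.3.2 sensitivity model with continuous DAS28 and change in DAS28. Let it answer whether factors beyond DAS28 jointly guide escalation. Keep the factor-wise estimates, including satisfaction, for individual impact.
2. As a presentation aid only, also report hazard ratios for the continuous factors at one fixed, stated increment, with 0-to-1 for binary terms. State that key factors will not be ranked on p-values or on per-unit size.

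The sign of the change indicator should be settled first. SAP 7.3.1 defines change as time point minus baseline and flags values above 1.8, which as written marks worsening, whereas Protocol 7.7 treats it as a response that lowers escalation. It determines what the four factors are adjusted for.

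Cost: one extra test and one table. No new data are needed and the fitted primary model does not change.
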